## 2. Survey of positioning and mobilization behavior

- Standardized observations (50) with n= 30-50
  - o Analysis by means of descriptive statistics (51)
  - o Behavior and attitude of mobilizing professionals will be observed (see appendix for topics of observation)
  - o In addition, the following data will be included in T2 and T3, which will be collected in the study arm "effects on patient outcomes":
    - o Ventilation (Yes / No)
    - o Medication (in Weaning → Yes / No; Analgosedation → Yes / No; Catecholamines → Yes / No )
    - o Gender
    - o Weight/ Height

Observation will only occur during mobilization of patients who have given consent to participate in the study.

Additionally, only mobilizing professionals who have given consent to participate in the study will be included in the observations and interviews. Should consent to the study be subsequently withdrawn at a later date, the study participants will be asked whether the data obtained up to that point may still be used. Otherwise, all the data collected up to that point will be destroyed.

### 8.3. DATA COLLECTION EFFECTS ON PATIENT OUTCOMES

In this study, various interventions will be performed on patients. All invasive procedures performed on patients will be performed as routine procedures independently of the study in the Intensive Care Unit (ICU) according to medical indication. The following study-related procedures will be performed on the patients beyond the informed consent and documentation of patient-related data:

Patients will receive robot-assisted mobilization within the first 72 hours after admission to the Intensive Care Unit  $\geq 2$  x / day for 20 minutes, for a minimum of ten treatment cycles or seven days. Clinical-functional examination with collection of clinical scores and ultrasound parameters on day -1, 1,2,3, then once a week if continued in the Intensive Care Unit, day 28, day of discharge from the Intensive Care Unit, 3 months after study inclusion (within the data collection period) (39).

No other study-related burdens or risks arise for patients.

An overview of clinical and study-related measures is provided below:

Measure	Measure performed	Specification/ Invasiveness
Education and informed consent	Study-related	Noninvasive
Clinical examination to determine physical function	Study-related	Noninvasive

Sonographic examination of the lungs, diaphragm, and M. quadriceps femoris	Study-related	Noninvasive
Early mobilization, robot-assisted	Study-related	Non-invasive within the framework of the CE-certified indication for approval
Documentation of patient-related data	Study-related	Noninvasive

In addition, personal data, laboratory values from clinical routine and clinical data are recorded:

Domain	Parameters
1. Personal Data	
	Age, sex, height, weight
Diagnosis	Admission and progressive diagnoses
Therapy	Medications, infusion solutions
2. Laboratory diagnostic data	
	Parameters determined from the routine
3. Clinical data	
SOFA score (52) Apache II score (41) SAPS II score (40) RASS(31) VAS GCS (36) Decubitus score according to Shea (37)	Temperature, mean arterial pressure, heart rate, respiratory rate, Oxygenation index, Blood pH, Lactate, Bicarbonate, Operative status, Glasgow Coma Score Chronic conditions, export urine See Scores
Acute renal failure	AKIN-Stadium
Data Organ replacement	Renal replacement procedures, ECMO therapy
Advanced hemodynamic monitoring	Cardiac index, zvO2... (if advanced hemodynamic monitoring such as pulmonary catheter or PICCO is established)
Invasive ventilation	Duration, ventilation parameters, CPaX-respiratory function (39)

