- (2) The behavior and experience of the mobilizing professionals will be evaluated using episodic interviews as well as standardized observations. Nurses with specialized training in anesthesia and intensive care, nurses and physiotherapists who have at least three years of professional experience in an intensive care unit as well as medical specialists who have completed their training as medical specialists or who have a leading position in an intensive care unit are included. In addition, the individuals have an employment contract at LMU Klinikum. Furthermore, the secondment to the anesthesiological intensive care units is an inclusion criterion.
- (3) The effects on patient outcomes, primarily duration of ventilation, muscle mass (sonographic examination) and physical activity (measured by established scores such as FSS-ICU and MRC classification), will be measured at different points in time and compared with a historical patient population. Secondary outcomes such as delirium incidence, hemodynamic parameters, respiratory parameters but also longitudinal parameters such as intensive care and hospital length of stay will be analyzed from routine data/patient records. Included are informed consenting patients who will undergo a planned surgical procedure that involves postoperative intensive treatment and an anticipated duration of ventilation of more than 48 hours. These patients will receive standardized early mobilization using the robotic system at either ten frequencies or for seven days. No invasive procedures such as blood sampling will be performed as part of the study. To evaluate the effect of robot-assisted VEM, the outcomes

will be compared with a historical comparison group. Approximately 30 patients shall be included. The results will be compared to a historical group (n=30) with conventional early mobilization.

The intervention is planned for a duration of five to six months starting in August 2021.

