## 5. TIMELINE OF THE STUDY

The study includes the period of early mobilization by robotic system of patients who meet the inclusion and exclusion criteria. These will be mobilized using the robotic early mobilization device twice a day for 20 minutes, at least ten times or within seven days. The data collection is planned for five to six months.

Within the study period, the following topics will be covered in three study lines (cf. fig. 4):

- (1) Feasibility of robot-assisted VEM in the Intensive Care Unit.
- (2) Behavior and experience of the mobilizing professionals
- (3) Effects on patients outcomes.

[figure not shown]

Figure 4: Overview of the time courses of the study arms.

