### 7.3. NUMBER OF PATIENTS

In order to test correlations using multiple-variate models (multiple linear regressions) with a statistical power of 80% on approximately 8 independent variables (UV) compared to the dependent variable (AV), an approximate total sample size of 50 subjects is required.

Thus, with an expected drop-out of 10%, 55 patients (robotic intervention and historical comparison group) should be included in the study. A sample size of 20 subjects is considered a lower limit with moderately strong associations between UVs and AV and inclusion of a maximum of 5 UVs, with  $\alpha=5\%$  and  $\text{power}=80\%$  (43, 44). In this regard, if 30-35 patients are included in the robot-assisted intervention and a maximum of 6 UVs, meaningful results can be expected to be obtained in a manageable period of time.

All patients will be included in the intervention only if written informed consent is obtained. Due to the expected patients' recruitment (6-8 patients/month) with a given number of cases (30-35 patients in the intervention), the study is expected to last five to six months from the start. The recruitment rate depends on the number of patients.

In general, all patients meeting the above-mentioned criteria will be included in the study. The study is completed as soon as the required number of patients has been recruited for the intervention. The corresponding number of cases for the historical group will be taken from the routine data.

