## 8. METHOD AND PROCEDURE

Patients of the LMU Hospital will be included according to the inclusion and exclusion criteria (see 5.2. and 5.3.). All patients who are to be treated surgically and whose postoperative care is planned in the anesthesiological intensive care units will be screened according to the inclusion and exclusion criteria. If the expected duration of postoperative ventilation exceeds 48 hours and there are no contraindications, the patient is given an information session. This should be done preoperatively with awake patients who are able of giving consent. In case of consent, the patient will be included in the study.

In addition, within the scope of the experience of the mobilizing specialists, nurses, physiotherapists, and physicians will be included according to inclusion and exclusion criteria, who are predominantly assigned to the intensive care units of the LMU Hospital and from T2 onwards to the anesthesiological intensive care units.

With the start of robot-assisted early mobilization, the survey will be conducted within the framework of organizational feasibility. This is carried out by project staff and ward staff. The survey ends with the last robot-assisted mobilization.

[figure not shown]

Fig. 5: Detailed procedure of the study with examination times of the patients

All patients will receive a physical examination at different time points to assess physical functionality and muscle strength, as well as a sonographic examination of leg muscles, diaphragm, and lungs. These examinations should be performed on day -1 (preoperatively), on postoperative days 1,2,3, then once a week if the patient remains in the Intensive Care Unit, on day 28, on the day of discharge from the Intensive Care Unit, and on a follow-up examination approximately 3 months after discharge from the Intensive Care Unit. The follow-up examination should only take place if the patients present themselves at the LMU Hospital anyway due to medically indicated follow-up examinations (not study-related). Alternatively, patients can be asked about their condition by telephone (see Fig. 5).

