#### Robot-assisted early mobilization

Patients included in the study according to the inclusion and exclusion criteria will be mobilized using the robotic system. The aim is to perform a standardized mobilization with verticalization within the first 72 hours after admission to the Intensive Care Unit. If possible, this should be performed twice every day for 20 minutes, with a minimum of ten treatment cycles or for seven days. Treatment characteristics such as timing, intensity, duration, and complications will be documented.

As part of the study, routinely collected personal data and laboratory chemistry data will also be documented. There will be no blood sampling or other invasive procedure as part of the study. The study period begins for the patients after their informed consent shortly before the surgical procedure and ends approximately 3 months after study inclusion with the planned follow-up examination, with the end of the recording period of the study or the death of the patient.

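### The 3-month follow-up is timed from two different starting points, and the five-to-six-month period, read literally, leaves late-enrolled patients no time to reach it

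*Protocol*

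**What the plan says.** **Length of the study.** Section 5 states: "The data collection is planned for five to six months". Section 7.3, from 30-35 intervention patients at 6-8 per month, concludes that "the study is expected to last five to six months from the start", and adds: "The study is completed as soon as the required number of patients has been recruited for the intervention". The Executive Summary attaches the same length to something else: "The intervention is planned for a duration of five to six months starting in August 2021".

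**Timing of the last visit, counted from inclusion.** Section 8.3 lists an examination "3 months after study inclusion (within the data collection period", with the parenthesis closing after those words. Section 8 (Robot-assisted early mobilization) says that a patient's study period starts with consent shortly before surgery and "ends approximately 3 months after study inclusion with the planned follow-up examination, with the end of the recording period of the study", or with death.

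**Timing of the last visit, counted from ICU discharge.** Section 8 (Method and procedure) schedules "a follow-up examination approximately 3 months after discharge from the Intensive Care Unit". The clinical examination part of Section 8.3 uses the same anchor and ties the SF-36 to it.

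**Conditions on the visit.** Section 8 (Method and procedure) adds: "The follow-up examination should only take place if the patients present themselves at the LMU Hospital anyway", that is, for medically indicated follow-up. It allows a telephone contact as the alternative.

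**What depends on it.** Section 4.3 lists the SF-36 after 3 months as a secondary outcome. The functional and sonographic examinations are also scheduled at this visit.

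**The concern.** There are two separate problems.

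First, one visit has two anchors. Because inclusion is preoperative, a date counted from inclusion falls earlier than one counted from ICU discharge by at least the ICU stay. That gap varies between patients and is longest for those who stay longest. The same visit could then be done at different points of recovery, depending on which section the study team follows.

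Second, the stated period appears to hold recruitment and nothing more. If the visit must fall inside that period, and participation may end when recording ends, the patients enrolled last cannot reach it. The missing data would then be concentrated in the late enrollees by design. This comes on top of drop-out, death and the condition that the in-person visit happens only when the patient attends anyway.

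**Working it through.** **Inputs.** Planned intervention patients n = 30-35 and rate r = 6-8 per month (Section 7.3). Window W = 5-6 months (Sections 5 and 7.3). Follow-up of 3 months from inclusion (Section 8.3). Accrual is assumed uniform from month 0.

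**Step 1. Reproduce the stated duration.** Accrual time A = n / r:

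- 30/8 = 3.75 months
- 35/8 = 4.38 months
- 30/6 = 5.0 months
- 35/6 = 5.83 months

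At 6 per month this gives 5.0-5.83 months, which is the protocol's five to six months. The figure is therefore recruitment time, with no follow-up added.

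**Step 2. Time for every patient to reach 3 months.** A + 3 = 6.75, 7.38, 8.0 and 8.83 months respectively. All exceed 6. Counting the first patient at day 0 shortens the best case only slightly: 29/8 + 3 = about 6.6 months. To fit into 6 months, accrual would have to finish in 3. That means no more than 8 × 3 = 24 patients at 8 per month, or a rate of 30/3 = 10 per month for 30 patients and 35/3 = 11.7 per month for 35.

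**Step 3. Patients who can reach exactly 3 months.** Reachable = r × (W − 3); lost = n − reachable.

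| n | r per month | W = 5: reachable, lost | W = 6: reachable, lost |
|---|---|---|---|
| 30 | 8 | 16, 14 (46.7%) | 24, 6 (20.0%) |
| 35 | 8 | 16, 19 (54.3%) | 24, 11 (31.4%) |
| 30 | 6 | 12, 18 (60.0%) | 18, 12 (40.0%) |
| 35 | 6 | enrolment does not finish (5.83 > 5) | 18, 17 (48.6%) |

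Over the combinations whose enrolment fits the window, 6-19 patients (20-60%) are lost.

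**Step 4. Sensitivity to a visit tolerance.** Most sections say that the interval is approximate but give no window. Assume, for illustration, that a visit up to 14 days early counts: 14/30.44 = 0.46 months. In the most favourable case (30 patients, 8 per month, 6 months), reachable = 8 × (6 − 3 + 0.46) = 27.7. The loss is (30 − 27.7)/30 = about 8%.

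**Step 5. Sensitivity to the anchor.** Counting from ICU discharge replaces W − 3 by W − 3 − (time from inclusion to ICU discharge), so the loss rises. The protocol gives no figure for that time, so I put no percentage on it.

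**The case against.** The strongest reply is that the protocol does not promise 3-month data from everyone. Section 8 names the end of recording as one of three ways in which participation ends, Section 8.3 restricts the visit to the data collection period, and the in-person visit is opportunistic. This stands: the cut-off is disclosed. What the protocol does not disclose is its size, and Section 4.3 lists the SF-36 without restriction.

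A second reply is that the Executive Summary ties the five to six months to the intervention, and that Figures 4 and 5, which may show the timing, are not visible here. A follow-up tail is therefore not excluded. This also stands, and it is why the point is confined to a literal reading of Sections 5 and 7.3. It does not touch the conflict of anchors.

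Several stronger readings are tempting but not supported:

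- *No stated sample size fits.* Section 7.3 also gives 20 subjects as a lower limit, and 20/8 + 3 = 5.5 months fits a 6-month window. That figure is a minimum for the regression and not the recruitment target, so the claim is limited to 30-35.
- *At least a fifth must be lost.* That needs exactly 3.0 months. Step 4 shows about 8% with an assumed tolerance.
- *All data collection stops on the day of the last enrolment.* The completion sentence in Section 7.3 could be read so, but the examination schedule in Section 8 runs beyond enrolment. The calculation does not use that reading.
- *The comparison with the historical group is damaged.* The primary patient outcomes are measured at ICU discharge or are ventilation time. Historical outcomes come from routine data, and no source for a historical SF-36 is described.

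The telephone option answers non-attendance. It does not answer the end of recording, and it cannot replace strength and ultrasound examinations.

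**Conclusion.** The concern holds as a minor point, in two parts.

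The conflict of anchors is textual and needs no assumption: two places count from inclusion and two from ICU discharge, for the same visit.

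The shortage of time holds on a literal reading of Sections 5, 7.3 and 8.3, for the planned 30-35 patients at 6-8 per month. All patients reaching 3 months after inclusion would take 6.75-8.83 months against a stated maximum of 6. With uniform accrual and exactly 3 months, about 12-24 patients could reach the visit before drop-out. A visit tolerance makes the loss smaller, and the ICU-discharge anchor makes it larger.

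The loss concerns the late enrollees' 3-month SF-36, functional and ultrasound data, and mainly weakens the description of the robotic group. Primary outcomes are unaffected.

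**What to change.** 1. Use one anchor for the 3-month visit in all four places (Section 8 Method and procedure, Section 8 Robot-assisted early mobilization, the schedule in Section 8.3, and its SF-36 paragraph), and state a visit window.
2. In Sections 5 and 7.3, say that five to six months is the enrolment and intervention period, and that reaching the required number closes enrolment, not follow-up. Without this step, the next one would create a new contradiction.
3. For the 3-month contact only, remove the restriction to the data collection period in Section 8.3 and the end-of-recording alternative in Section 8, so that the contact runs to the last patient's 3-month date. Collect the SF-36 through the telephone contact already allowed from patients who do not attend.

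If the end date is fixed, state instead that 3-month outcomes are expected only from patients included about 3 months or more before the end (about 12-24 of 30-35 before drop-out), and that they are descriptive. The anchor still has to be reconciled.

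**Cost.** Wording changes; the ethics committee consultation that the protocol requires for amendments; about 6-19 further contacts, many of which could be by telephone; and longer participation for late enrollees. The 3-month results would come 0.75 months (6.75 − 6) to 3 months (8.0 − 5) later. Primary analyses need not wait.

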### *Individual measures during study procedure*

### *Education and Informed consent*

Only patients who are capable of giving consent and can be informed preoperatively will be included. Informed consent will be obtained from all patients who meet the other inclusion criteria. If the patients withdraw their consent to the study at a later point in time, they will be asked whether the data collected up to this point in time may still be used. Otherwise, all data collected up to that point will be destroyed. There is no intention to include persons from the group of persons in need of special protection.

### *Clinical examination to determine physical function/ health-related quality of life.*

To assess physical function and muscle strength, the following non-invasive examinations will be performed and/or scores will be collected as required by the study:

FSS-ICU (53): the FSS-ICU assesses the patients "Physical Performance" based on 5 factors. For each of the 5 tasks, a minimum of 0 to a maximum of 7 points can be assigned. The following table summarizes the individual tasks.

Task	Score
1. Turning	
2. Transition from lying to sitting	
3. Transition from sitting to standing	
4. Sitting at the edge of the bed	
5. Walking	
Total score	

MRC (Medical Research Council) classification on upper and lower extremity:

Assessment of the degree of strength using the MRC classification is widely used and follows the well-known classification (see table below):

	Degree of Strength
Absence of muscle contraction	0
Visible muscle contraction	1
Movement with elimination of gravity	2
Active movement against gravity	3
Active movement against resistance	4
Normal force	5

At the follow-up examination approximately 3 months after discharge from the intensive care unit, the health-related quality of life will also be assessed using the SF-36 questionnaire (34).

*Sonographic examination of the lungs, diaphragm and Musculus quadriceps femoris*

Part of the examination is the sonographic evaluation of the diaphragm, lungs and Musculus quadriceps femoris.

These will be briefly illustrated with reference to Figures 6-8.

[figure not shown]

Figure 6: Landing points sonography lung: quantification of diaphragm thickness is performed on the right side of the body, where the diaphragm approaches the thoracic wall in the region of the liver (so-called apposition zone) (38, 54).

To determine the thickening fraction, the diaphragm thickness is determined in inspiration and in expiration (55).

[figure not shown]

Fig. 7: Assessment of diaphragmatic excursions: Using a submammary plumb line (left image), the liver is first visited on the right side of the body as a sonic window (middle image). The diaphragmatic excursions are quantified using the M-mode (right image). On the left side of the body, the spleen is used as a sonic window (not shown).

The Musculus quadriceps femoris will be quantified using cross sectional area and thickness (56, 57). The principle of the examination is shown in Figure 8.

[figure not shown]

Fig. 8: left: Sonographically determined thickness of the M. quadriceps femoris on the right thigh in B-mode. Measurement points: Femur bone (+) and the posterior border of the Fascia Lata (+1). Right: Sonographically determined cross sectional area of the Musculus rectus femoris. RF, rectus femoris; VL, vastus lateralis; VM, vastus medialis; VI, vastus intermedius (57).

### Robot-assisted early mobilization

The patient group will be early mobilized using robot-assisted therapy. Robot-assisted early mobilization is performed only if it is deemed safe to perform according to the criteria and recommendations of the Consensus Conference (58). This Consensus Manuscript provides recommendations on the conditions under which safe active mobilization is feasible in ventilated patients. It considers four categories (respiratory, cardiovascular, neurological, other). In this study, patients should only be robot-assisted if this is in accordance with the recommendations - level green or yellow - (see Fig. 7). Since transferring to a therapy device as described is not required for mobilization with the VEMO© system, the mobilization is categorized as "in-bed-exercise" (versus out-of-bed mobilization). The criteria are discussed with the ward team prior to each robot-assisted mobilization.

[figure not shown]
	Low risk of an adverse event. Proceed as usual according to each ICU's protocols and procedures.
	Potential risk and consequences of an adverse event are higher than green, but may be outweighed by the potential benefits of mobilization. The precautions or contraindications should be clarified prior to any mobilization episode. If mobilized, consideration should be given to doing so gradually and cautiously.
	Significant potential risk or consequences of an adverse event. Active mobilization should not occur unless specifically authorized by the treating intensive care specialist in consultation with the senior physical therapist and senior nursing staff.

Figure 9: Traffic light system (59): In the patient group, robot-assisted mobilization is only performed if the risk assessment is green; if the risk assessment is yellow, a critical risk-benefit assessment is performed with the ward team and a graduated mobilization is performed. In the case of a red risk assessment, no active robot-assisted mobilization takes place.

The adaptive robotic system VEMO© enables early mobilization of even the most severely ill patients (see Fig. 10). These can be verticalized with the bed up to 70° degrees. Here, a leg movement can be generated according to gait patterns.

The treatment team does not differ for the individual patients: it usually consists of nurses from the corresponding intensive care units, assigned physiotherapists and the corresponding ward physicians. For the duration of the study, an additional study team will be established, consisting of study physicians, study nurses and technical support from the manufacturer.

Robotic-assisted early mobilization should be performed within the first 72 hours postoperatively, if possible, and should be performed at least twice a day for 20 minutes until the seventh postoperative day or at least ten cycles of treatment during the intensive care unit stay.

Frequency of treatment, treatment duration and intensity are recorded. Treatment-associated events will be recorded.

In case of hemodynamic, respiratory or other instability during treatment, the therapy session can be discontinued at any time. The decision to discontinue mobilization rests solely with the treatment team. The study team can advise.

Fig. 10: Robot-assisted verticalization with VEMO©.

